## Table 7. Procedures for HIV seroconverters among HIV-negative male partners who initiatePrEP

HIV-negative men who seroconvert to HIV will have one set of samples collected as close in time to the seroconversion visit as possible (ideally, either at the SC or SC<1 month visits). Samples to be collected are:

CD4 count Viral load Plasma archive (for tenofovir and resistance assays)

STATISTICAL ANALYSIS PLAN

VERSION: 1.0

DATE OF PLAN:

08 October 2021

BASED ON:

Version 3.1, 17 March 2019

STUDY TITLE:

HIV SELF-TESTING AND PREP TO INCREASE TESTING AND PREVENTION UPTAKE AMONG MALE PARTNERS AND IMPROVE POSTPARTUM ART USE IN PMTCT B+ PROGRAMS IN UGANDA

SPONSOR:

ICRC

Funding:

United States National Institute of Mental Health

(R01 MH113434)

This study is being conducted in compliance with good clinical practice, including the archiving of essential documents.

30 Sep 2021

SIGNATURE PAGE

This document has been prepared and/or reviewed by:

[name]

[name]

Oct 11, 2021

Project Statistician

Signature

Date

This document has been reviewed and accepted by:

[name]

Protocol Chair, ICRC

Signature

Date

PROTOCOL SUMMARY

Title Of Study: HIV self-testing and PrEP to increase testing and prevention uptake among male partners and improve postpartum ART use in PMTCT B+ programs in Uganda	
Investigators: Study Center(s): Infectious Diseases Institute (IDI) Kasangati and collaborating antenatal care (ANC) clinics in Kampala, Uganda	
Studied period (years): 2 years	Phase of development: Randomized implementation study
Objectives: Aim 1: Determine whether an enhanced PMTCT program with HIV self-testing for male partners and provision of PrEP to HIV-negative male partners increases the proportion of male partners who test for HIV, and HIV-negative men who initiate PrEP or HIV-positive men who start ART. Aim 2: Evaluate whether HIV testing combined with PrEP and ART use among male partners increases effective post-partum ART use among HIV-infected Ugandan women in PMTCT B+. Aim 3: Assess the acceptability of HIV self-testing and PrEP to pregnant women taking part in PMTCT B+ and to their male partners, using qualitative and quantitative methods.	
Methodology: Pregnant women ≥18 years accessing ANC and PMTCT B+ programs in Kampala, who have a male partner of unknown HIV status will be randomized to the intervention (HIVST) or the control arm. Women will be instructed in the use and interpretation of HIVST and be provided two HIVST kits to give to or use with their male partners. We will recommend that HIV-negative partners in couples (either HIV negative male partners of HIV-positive pregnant women) or HIV-negative pregnant women with an HIV positive male partner) use PrEP until their partner has been on ART for at least 6 months and achieved viral suppression, and that HIV-positive partners take ART.	

1. INTRODUCTION

The purpose of this document is to provide details on study populations and on how the variables will be derived, how missing data will be handled as well as details on statistical methods to be used to analyze the study data

This SAP addresses the statistical analyses of Aims 1 and 2, and selected secondary objectives.

2. STUDY OBJECTIVES AND ENDPOINTS

2.1. Study Objectives

2.1.1. Primary Objectives

- Assess whether an enhanced PMTCT program with HIV self-testing for male partners increases the proportion of male partners who test for HIV compared to standard of care information letter about HIV testing for male partners.
- Assess whether the HIV self-testing strategy for male partners affects the proportion male partners who initiate HIV/ART, and the proportion of HIV-negative men who begin PrEP.

2.1.2. Secondary Objectives

- Evaluate whether HIV testing combined with offer of PrEP for HIV-negative male partners and ART uptake for HIV-infected male partners increases effective post-partum ART use among HIV-infected Ugandan women in PMTCT B+.
- As a women's HIV disclosure to her partner is hypothesized to be the mechanism for increasing her effective ART use, we will evaluate associations between first visit a women reported disclosure of their HIV-infected status to their male partner and the trial endpoints: enrollment of the male partner, uptake of PrEP/ART; viral suppression. We will also assess whether male partner testing, HIV status and disclosure, impact trial endpoints.

2.2. Study Endpoints

2.2.1. Primary Endpoints

Aim 1a

- Time to HIV testing and enrollment of the male partner (male partners come to the site to receive HIV testing during enrollment). Male partners who do not enroll are assumed

30 Sep 2021

to not know their HIV status. HIV-infected partners who are on ART at enrollment are omitted from the analysis (not at risk for ART initiation)

Aim 1b

- Time to initiation of PrEP/ART for male partners:
 - Amongst all women
 - Time to enrolled male partner with known HIV status initiating PrEP/ART (Male uptake of PrEP/ART). If the male partner is not enrolled he is defined as unknown HIV status (to his partner), and assumed not on PrEP/ART.
 - Time to enrolled male partner who started ART /PrEP or has female partner who is VS (Couple use of ART/PrEP). VS of the woman is defined as VS at both the prior and subsequent visit
 - Amongst women with enrolled partners,
 - PrEP initiation in enrolled HIV-negative male partners or ART initiation in enrolled HIV-positive partners
 - PrEP initiation OR undetectable VL of female partners in enrolled HIV negative male partners
 - Couple use of ART/PrEP (ART use in enrolled HIV-positive male and female partner or PrEP initiation in HIV-uninfected partners. An alternative (stricter) definition of ART use may also consider the biomarker viral suppression)

Aim 1c

- Time to initiation of PrEP for male HIV-uninfected partners:
 - Amongst women with enrolled partners
 - Time to enrolled male partner with known HIV-negative status initiating PrEP.
 - Time to enrolled HIV-uninfected male partner who started PrEP or has female partner who is VS (Couple use of ART/PrEP). VS of the woman is defined as VS at both the prior and subsequent visit

Aim 2a

- Viral load suppression (Defined as VL < 400 copies) at 12 months post-partum amongst enrolled women.

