5. GENERAL CONSIDERATIONS FOR DATA ANALYSES AND HANDLING

5.1. Analysis Populations

5.1.1. ITT Population

The ITT women population is all women enrolled and randomized into the study. Women are pregnant and HIV-infected and do not know their male partner's status.

The ITT male partner population includes male partners of all women enrolled and randomized into the study. Male follow-up begins at the time of their enrollment and ends when their partner reaches 12 months post-partum,

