5.2.2. Use in analysis

Key predictors

- 1) Study arm: HIVST (Intervention arm) versus Letter (standard of care arm). Assigned at randomization of the women.

30 Sep 2021

- 2) Partner enrolled (time varying): whether male partner was enrolled prior to the current visit.
- 3) Uptake of PrEP/ART of partner (time varying):
 - a. A woman has a partner with PrEP/ART uptake at her visit if her partner knows his HIV status and is either on ART (if HIV-positive) or initiated PrEP (if HIV-negative) prior to that visit. Both male partners who do not enroll and male partners who do not initiate ART or PrEP are defined as no uptake of PrEP/ART. In analyses that use time to PrEP/ART, time of first report of PrEP/ART will be used.
 - b. An alternative definition will also define any HIV-negative men with partners who are virally suppressed as on PrEP/ART. A female partner is defined as being VS if she is virally suppressed at assessments both before and after the visit.
- 4) Disclosure of HIV-infected status to male partner self-reported at baseline

Effect modifiers:

- 1) Viral suppression of woman (time varying, measured at baseline, 6 and 12 mo)
- 2) Trimester of pregnancy at enrollment
- 3) Partner ever tested for HIV (time varying: reported by female partner)
- 4) Mutual disclosure status of HIV (time varying, as reported by each partner). If no enrolled male partner, mutual disclosure is assumed to not occur.
- 5) Male HIV status. If a male partner does not receive HIV testing from the study site, it is assumed their HIV status is unknown to both members of the coupleStudy Population

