7.3. Analysis of the Primary Endpoints

7.3.1. Aim 1a Difference in male partner testing between arms

Endpoint: HIV testing at the study site of a woman's male partner. HIV testing at the site is synonymous with male partner enrollment.

Descriptive analyses:

- We will tabulate the proportion of women with male partner enrollment by the end of the study by arm, and the resulting HIV status (by study testing) of the male partners at enrolment.
- We will tabulate the proportion of men who have been HIV tested, and their HIV test result, according to the women's self-report, by arm. Note that as the HIVST arm provides a test for men at home, this comparison has potential for ascertainment bias.

Statistical analysis

We will use Kaplan-Meier curves to depict the time from women's enrollment until her male partner's site HIV test (i.e. enrollment) by study arm.

We will assess the difference between arms using a time to event analysis of time of randomization of the pregnant women until the event of her male partner's HIV test at enrollment. A Log-rank test will be used to assess the statistical significance of difference between arms; Cox proportional hazard regression will be used to estimate the HR and 95% CI. The Kaplan Meier curve will be used to assess the proportion of male partners tested at 6 and 12 months after female partner randomization. Pointwise confidence intervals will be computed assuming the normal approximation, using the standard error of the estimate from the KM curve.

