7.3.2. Aim 1b Difference in uptake of PrEP/ART for male partner between arms

Endpoint: Enrolled male partner of an enrolled women initiates PrEP, if he is HIV-uninfected, or initiates ART, if he is infected.

Descriptive analysis.

- We will tabulate the proportion of women whose male partner initiates PrEP/ART by the end of the study, and report initiation of PrEP/ART separately by HIV-status of the male partner

30 Sep 2021

- Amongst the enrolled male partners, we will tabulate the proportion of HIV-infected men who initiate ART, and HIV-uninfected men who initiate PrEP, within each arm, by the end of the study.
- HIV+ men who are on ART at time of study enrollment will be omitted from this analysis

Statistical analysis

We will use Kaplan-Meier curves to depict the time from women's enrollment until her male partner has initiated PrEP/ART by study arm.

We will assess the difference between arms using a time to event analysis of from time of randomization of the woman until the event of her male partner initiating PrEP/ART. For women who never have a partner enroll, the male partner remains at risk for the event throughout the woman's follow-up; time will be censored at the woman's last observed visit. Women with partners already on PrEP/ART with the partner enrolled are not at risk and are omitted from the analysis. Log-rank test will be used to assess the statistical significance of difference between arms; Cox proportional hazard regression will be used to estimate the HR and 95% CI. The Kaplan Meier curve will be used to assess the proportion of male partners who initiate PrEP/ART 6 and 12 months after female partner randomization. Pointwise confidence intervals will be computed assuming the normal approximation, using the standard error of the estimate from the KM curve.

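### Partners already on ART: SAP 2.2.1 and 7.3.1 disagree on whether they count in Aim 1a, and SAP 7.3.2 drops a randomised woman from Aim 1b only if such a partner enrols, so that set is not ITT

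*SAP*

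**What the plan says.** **Aim 1a.** SAP 2.2.1 defines the endpoint as time to the male partner's testing and enrolment, then adds "HIV-infected partners who are on ART at enrollment are omitted from the analysis (not at risk for ART initiation"). SAP 7.3.1 states "HIV testing at the site is synonymous with male partner enrollment", runs time from the woman's randomisation to that test, and mentions no omission.

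**Aim 1b.** SAP 7.3.2 states "Women with partners already on PrEP/ART with the partner enrolled are not at risk and are omitted from the analysis". Its descriptive analysis likewise leaves out HIV-positive men on ART at enrolment. For the rest it says "For women who never have a partner enroll, the male partner remains at risk for the event throughout the woman's follow-up", and 2.2.1 adds "If the male partner is not enrolled he is defined as unknown HIV status (to his partner), and assumed not on PrEP/ART". Section 2.2.1 labels this comparison as covering all women.

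**Elsewhere in the SAP.** Section 5.1.1: "The ITT women population is all women enrolled and randomized into the study". Section 5.2.2 counts a woman's partner as having uptake if he "is either on ART (if HIV-positive) or initiated PrEP (if HIV-negative) prior to that visit", and adds "In analyses that use time to PrEP/ART, time of first report of PrEP/ART will be used". Section 7.3.4 (Aim 2a) includes men who were on ART when they enrolled.

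Men already on ART can be in the cohort. Eligibility (protocol Eligibility; SAP protocol summary) requires that the partner is not known to be HIV-positive, or has not tested in the past 3 months.

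**The concern.** An on-ART man who comes to the site and enrols has had the Aim 1a event. Removing him because he cannot start ART applies the logic of Aim 1b to a testing endpoint. The sentence is probably an Aim 1b rule in the wrong place. As written, though, a programmer following 2.2.1 and one following 7.3.1 would analyse different sets of women for a protocol co-primary outcome.

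Aim 1b has a structural problem. Take two women whose partners were both on ART at randomisation. The one whose partner enrols is deleted; the one whose partner stays away is kept as a non-event. Enrolment happens after randomisation and is itself the Aim 1a outcome, so the arms can lose different fractions of women for reasons the intervention causes. SAP 7.3.3 recognises that the intervention may alter enrolment differently by HIV status and adds an estimate for Aim 1c that does not condition on enrolment. Aim 1b has no such estimate.

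The rule is also tied to the man's own enrolment date. A man who self-tests, starts ART elsewhere and then enrols is deleted, although he started after randomisation.

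**Working it through.** **The plan's own figure.** In the second table of SAP 3.2.1, the row with 60% HIV-negative and testing 30% vs 55% gives uptake of 26% vs 48%. Uptake = test uptake × (0.60 × 0.80 + 0.40 × 1.00) = 0.88 × test uptake, which is 26.4% and 48.4%. It reproduces, with every woman in the denominator and nobody omitted.

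**Inputs.** From the documents: 500 women randomised 2:1 (about 333 HIVST, 167 letter), site testing 55% vs 30%, 60–70% HIV-negative, 80% PrEP uptake, 100% ART uptake, two-sided 0.05. Assumed, because the documents are silent: 25–75% of HIV-positive partners are already on ART, with the same share among attenders in both arms.

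**Formulas.** Let s = share site-tested and e = s × HIV-positive × on-ART.
- HR = ln(1 − p_HIVST) / ln(1 − p_letter).
- Aim 1a with the 2.2.1 omission: p = (s − e)/(1 − e).
- Aim 1b initiation: i = s × [HIV-negative × 0.8 + HIV-positive × (1 − on-ART)]. Deletion gives i/(1 − e), non-event gives i, and uptake gives i + e.

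**Aim 1a.** Without omission: 55% vs 30%, HR ln(0.45)/ln(0.70) = 2.24, difference 25.0 points. With omission, HIV-positive share widened to 30–50%: 14–69 vs 4–19 women dropped, HR 2.27–2.39, difference 24.7–22.2 points. Power (normal approximation, two proportions) stays above 99%.

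**Aim 1b, mid case** (60% HIV-negative, half of HIV-positive men on ART): e = 0.55 × 0.4 × 0.5 = 11% vs 6%, so 37 vs 10 women are deleted; i = 0.55 × 0.68 = 37.4% vs 20.4%.

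| Handling of on-ART men | HIVST | Letter | Difference | HR |
|---|---|---|---|---|
| Deleted (7.3.2) | 42.0% | 21.7% | 20.3 | 2.23 |
| Kept as non-events | 37.4% | 20.4% | 17.0 | 2.05 |
| Counted as uptake (5.2.2) | 48.4% | 26.4% | 22.0 | 2.16 |

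The last row is the quantity in the planning table. Across 60–70% HIV-negative and 25–75% on ART, deletion removes 14–55 vs 4–15 women and gives HR 2.17–2.27 and 19.1–21.3 points. Non-event gives 2.01–2.10 and 14.5–19.6 points. Uptake gives 2.15–2.16 and 21.5–22.0 points.

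**Null case for Aim 1b.** On-ART men are 20% of partners, 30% of all other men enrol in both arms, and 20.4% of women have a partner who initiates in both arms. In the letter arm 30% of on-ART men enrol, so deletion gives 0.204/(1 − 0.06) = 21.7%. In the HIVST arm it gives 0.204/(1 − 0.2 × share enrolling). Rejection rates are from 20,000 simulated trials per scenario (constant hazards over 1 year, log-rank, Monte Carlo SE at most 0.22 points).

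| On-ART men enrolling, HIVST vs letter | HIVST after deletion | HR | Rejection |
|---|---|---|---|
| 40% vs 30% | 22.2% | 1.02 | 5.0% |
| 55% vs 30% | 22.9% | 1.06 | 5.9% |
| 75% vs 30% | 24.0% | 1.12 | 7.6% |
| 90% vs 30% | 24.9% | 1.17 | 11.1% |

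Keeping these women as non-events gave 4.7–5.1% in the same runs.

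**ART started elsewhere before enrolling.** Mid case; suppose 10–50% of the HIVST-arm attenders who are HIV-positive and not on ART at randomisation do this (0.55 × 0.4 × 0.5 = 11% of women), and none in the letter arm. Then 4–18 women with a true initiation are deleted. HR is 2.18–1.97 with deletion, 1.98–1.68 if every man on ART at enrolment is a non-event, and 2.05 if these initiations are counted.

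**The case against.** The Aim 1a conflict is by silence: 7.3.1 simply states no omission, and the sentence in 2.2.1 looks like a drafting slip. For Aim 1b, 7.3.2 gives its rule twice and clearly, so the 17.0 and 22.0 point figures apply definitions that section did not adopt. Section 5.2.2 defines a predictor, and Aim 2a uses partner status as an exposure, so including men already on ART there is natural. The SAP does not expressly assign the ITT set to Aim 1b, which is a SAP primary endpoint but not a protocol co-primary. The on-ART range has no source: at 10% of HIV-positive men (60% HIV-negative) only about 7 vs 2 women are dropped and the three differences are 21.7, 21.0 and 22.0 points. The inflated null scenarios need kits that draw in on-ART men and nobody else.

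Much of this stands on size. The effect is modest, and it is negligible if few partners are on ART. The contrast with Aim 2a is weak evidence of inconsistency. The objection does not remove the main points. Clear wording in 7.3.2 does not repair a set chosen on a post-randomisation event under a label of all women. Section 2.2.1 calls the Aim 1b outcome male uptake, and the first-report rule in 5.2.2 covers analyses of time to PrEP/ART, so the SAP does point to a second way of counting these men. Silence in 7.3.1 is informative because 7.3.2 states an omission where one is intended.

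**Conclusion.** The concern holds. Aim 1a has two incompatible definitions. Aim 1b, followed as written, excludes women on the basis of an outcome the intervention targets. These are findings on the text and do not depend on any assumed number.

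The size does depend on the unknown on-ART share. At 25–75% of HIV-positive men, applying the 2.2.1 sentence raises the Aim 1a HR slightly and shrinks the difference by at most about 3 points. The Aim 1b difference moves by several points with the handling rule. If on-ART men are the same share of site attenders in both arms, the null stays valid. A false arm effect needs their enrolment to differ by arm, and reaches 7.6–11.1% rejection only at gaps of 75–90% vs 30%. It should be fixed because the reported effect ought not to turn on an ambiguous or post-randomisation exclusion, not because the trial's conclusion is likely to reverse.

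**What to change.** 1. **Aim 1a.** Delete the omission sentence from SAP 2.2.1. Analyse every randomised woman and count any site test as the event, as 7.3.1 already does.
2. **Aim 1b.** Keep every randomised woman and define two outcomes.
   - *Linked and on PrEP/ART*: being on ART counts as uptake, as in 5.2.2.
   - *Initiation*: PrEP, or ART started after the woman's randomisation where the start date shows it, is an event. ART started before randomisation is a competing event or a non-event; choose one in advance. Compare cumulative incidence by arm.
3. Show the current deletion only as a sensitivity analysis.

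The cost is SAP wording and a little more analysis. There are two drawbacks. Initiation relies on the man's reported ART start date, and the documents do not say that it is recorded: protocol Table 6 lists a medical history at his enrolment, and SAP 5.2.2 uses first report. Where the date is missing, show both extremes. The linked outcome also rises if kits merely bring in more men already on ART. With equal initiation of 20.4% and on-ART men (20% of partners) enrolling 55% vs 30%, it is 31.4% vs 26.4%, HR 1.23, so it must not be reported as initiation.

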3.4. Assessments

3.4.1. Male visit schedule:

Every three months after enrollment up to 12 month post-partum. Men will undergo informed consent for HIV testing and referral for HIV care and ART if they test HIV-positive, or offered PrEP if they test HIV-negative.

3.4.2. Pregnant women schedule:

Antenatal visit schedule to align with the PMTCT schedule. One visit expected every trimester. Study visits occur every three months after birth (post partum). Viral load (VL) monitoring will include plasma HIV RNA levels at enrollment, 6 and 12 months post-partum.

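### SAP 2.2.1, Aim 1b: the all-women couple-use endpoint lets a woman's viral suppression count for an HIV-positive man not on ART, contrary to the SAP's other definitions

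*SAP*

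**What the plan says.** SAP 2.2.1 gives two Aim 1b time-to-event endpoints for all women. The first is the man's own uptake of PrEP or ART. The second is couple use: "Time to enrolled male partner who started ART /PrEP or has female partner who is VS (Couple use of ART/PrEP". Its VS rule is "VS of the woman is defined as VS at both the prior and subsequent visit".

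The same idea appears elsewhere in the SAP with different content:

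- 2.2.1, Aim 1b, enrolled partners: "PrEP initiation OR undetectable VL of female partners in enrolled HIV negative male partners".
- 2.2.1, Aim 1b, enrolled partners, again labelled couple use: "Couple use of ART/PrEP (ART use in enrolled HIV-positive male and female partner or PrEP initiation in HIV-uninfected partners".
- 2.2.1, Aim 1c: "Time to enrolled HIV-uninfected male partner who started PrEP or has female partner who is VS (Couple use of ART/PrEP".
- 5.2.2, key predictor 3b: "An alternative definition will also define any HIV-negative men with partners who are virally suppressed as on PrEP/ART", with the timing rule "A female partner is defined as being VS if she is virally suppressed at assessments both before and after the visit".
- 7.3.2, the Aim 1b analysis: an uninfected man must initiate PrEP and an infected man must initiate ART. VS is not mentioned.

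SAP 3.4.2 schedules viral loads as "plasma HIV RNA levels at enrollment, 6 and 12 months post-partum".

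**The concern.** The primary objective in SAP 2.1.1 concerns men who start ART or PrEP. A woman's suppression can reasonably stand in for PrEP when the man is HIV-negative, because it bears on his exposure. It does not stand in for an HIV-positive man's own treatment. With the VS route open to all enrolled men, a man who tested positive and was never linked to ART is scored as a success. One who starts ART later may be credited before his own start.

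There is also a timing problem. VS at the time of the event requires a suppressed viral load taken afterwards, so event status depends on data that do not yet exist at that time, and on the woman being retained until then. The SAP gives no event date for the VS route.

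**Working it through.** **Definitions compared.** Take an enrolled HIV-positive man, not on ART, whose partner meets the VS rule.

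| Place in SAP | Does he have the event? |
|---|---|
| 2.2.1 Aim 1b, all women, couple use | Yes |
| 2.2.1 Aim 1b, all women, male uptake | No |
| 2.2.1 Aim 1b, enrolled partners, VS bullet | No, HIV-negative men only |
| 2.2.1 Aim 1b, enrolled partners, couple use | No, he must use ART |
| 2.2.1 Aim 1c | No, HIV-uninfected men only |
| 5.2.2 item 3b | No, HIV-negative men only |
| 7.3.2 endpoint | No, he must initiate ART |

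One definition stands alone, and it shares its label with another that contradicts it.

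**Plan's own figures.** The SAP gives no event count or power for couple use. The neighbouring male-uptake figures in SAP 3.2.1 do reproduce. With 60% of men HIV-negative, 80% PrEP uptake and 100% ART uptake, uptake per tested man is 0.6 × 0.8 + 0.4 × 1.0 = 0.88. Then 0.20 × 0.88 = 17.6% (stated 18%) and 0.55 × 0.88 = 48.4% (stated 48%).

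**HIV-positive men tested**, from the row pairings in Protocol Table 4 (500 × test uptake × HIV prevalence):

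- 500 × 0.43 × 0.4 = 86
- 500 × 0.47 × 0.3 = 70.5
- 500 × 0.50 × 0.4 = 100
- 500 × 0.53 × 0.3 = 79.5

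This gives about 70-100 men.

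**Men wrongly credited** = HIV-positive men tested × share not starting ART × share of partners suppressed. The share not starting ART is my assumption, 10-30%. Suppression runs from 50% (the Protocol's Aim 2 planning value when the man starts neither drug) to 90% (the Protocol background figure for women on ART for more than 6 months).

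- Low: 70 × 0.10 × 0.50 = 3.5, about 4
- High: 100 × 0.30 × 0.90 = 27

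**Effect on the endpoint among enrolled men** (60% HIV-negative, 80% PrEP uptake, ART uptake a, women's suppression v):

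- VS route for HIV-negative men only: 0.6 × (0.8 + 0.2v) + 0.4a
- As written: 0.6 × (0.8 + 0.2v) + 0.4 × (a + (1 − a)v)

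| ART uptake a | As written, v = 50% to 90% | Restricted, v = 50% to 90% |
|---|---|---|
| 100% (SAP) | 94.0-98.8% | 94.0-98.8% |
| 90% (assumed) | 92.0-98.4% | 90.0-94.8% |
| 80% (assumed) | 90.0-98.0% | 86.0-90.8% |

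**Effect on the arm comparison**, at 55% versus 30% testing, a = 80%, v = 90%, equal in both arms:

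- As written: 0.98 × 0.55 = 53.9% versus 0.98 × 0.30 = 29.4%; risk ratio 1.83; exponential hazard ratio ln(0.461)/ln(0.706) = 2.22
- Restricted: 0.908 × 0.55 = 49.9% versus 0.908 × 0.30 = 27.2%; risk ratio 1.83; hazard ratio ln(0.501)/ln(0.728) = 2.18

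**Timing.** A man who enrols just after his partner's month-6 viral load waits about 6 months for the value that settles his status. After month 12 no viral load is scheduled.

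**The case against.** The best defence is that 7.3.2 is the operative text for Aim 1b. It requires an infected man to initiate ART and has no VS route, so the only specified Aim 1b analysis does not make the error. That stands and limits the consequence. But couple use is still listed as a primary endpoint, and without matching analysis text the choice of definition is left open.

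It is also fair that at the SAP's 100% ART uptake nobody is wrongly credited in the final proportion. Only the timing could then be affected.

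Stronger readings are tempting but not supported:

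- *The kit arm gains an unfair advantage.* A reader might note that (333 × 0.55)/(167 × 0.30) = 3.7 times as many wrongly credited men fall in that arm. Most of this is the 2:1 allocation. Per woman the ratio is 0.55/0.30 = 1.83, which is the assumed testing effect itself. The documents give no figures for ART uptake or suppression that differ by arm.
- *Suppression is dated from the later viral load.* The SAP does not say so; it gives no date for this route.
- *A couple lacking the next scheduled viral load can never qualify.* SAP 5.3 carries values from adjacent visits within about 3 months, and 7.3.4 and 7.3.5 use month-9 and month-3 values for missing month-12 and month-6 ones. Missing values are partly covered, although the latter two rules are written for Aim 2.
- *Half of HIV-positive men go untreated.* The Table 4 counts reproduce with 50% on ART, for example 250 × (0.6 × 0.8 + 0.4 × 0.5) = 170. But the footnote calls this ART persistence and does not say whose, so it is not an initiation rate.

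Finally, the before-and-after rule has a purpose. Relying on the latest earlier value could classify a man by a viral load from his partner's pregnancy that is many months old.

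**Conclusion.** The all-women couple-use endpoint in Aim 1b is wrong as worded and inconsistent with the rest of the SAP. The size is modest: about 4-27 men, given 70-100 HIV-positive men tested, 10-30% not starting ART (assumed) and 50-90% of women suppressed. Men already on ART at enrolment are omitted under 7.3.2, which lowers the count by an amount the documents do not give. Requiring suppression at two assessments lowers it further.

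The harm is to meaning. The endpoint drifts towards a restatement of enrolment and says less about linkage. Material bias between arms is not shown: with equal ART uptake and suppression by arm, the risk ratio is unchanged and the hazard ratio moves only from about 2.18 to 2.22.

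The dependence on a later viral load is real in Aims 1b and 1c. It calls for a stated event date and a sensitivity analysis, not replacement of the rule.

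**What to change.** In SAP 2.2.1, Aim 1b, all women, reword the couple-use bullet by HIV status: an enrolled HIV-positive man has the event when he starts ART; an enrolled HIV-negative man has it when he starts PrEP or when his partner meets the VS definition. This agrees with 5.2.2 item 3b and Aim 1c. Give the two couple-use definitions different labels, or make them one, and say in 7.3.2 how the endpoint is analysed.

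For the VS route in Aims 1b and 1c, state the event date. Add a sensitivity analysis that defines VS from the most recent viral load on or before that date, keeping the before-and-after rule as the main definition.

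The cost is a few lines of SAP text and one extra derived variable. The rewording gives slightly fewer events. The sensitivity analysis may rest on old values, which is why it should not replace the main rule.
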